# 5.0 TREATMENTS ADMINISTERED

**5.1 Inotuzumab ozogamicin**, the investigational agent under study in this protocol, is an ADC comprised of a humanized IgG4 monoclonal antibody (G5/44) that recognizes CD22 antigen and is covalently linked via an acetyl butyrate linker to N-acetyl- $\gamma$ -calecheamicin dimethyl hydrazide (CalichDMH), a semisynthetic derivative of calecheamicin.

Detailed information describing the preparation, administration, and storage of inotuzumab ozogamicin is located in the Pharmacy Manual.

# 5.1.1 Description

Inotuzumab ozogamicin is a white to off-white powder or cake, lyophilized, unpreserved 4-mg protein equivalent powder for intravenous injection in an amber vial supplied by Pfizer.

# 5.1.2 Dose and Administration

Inotuzumab ozogamicin must not be administered as an IV push or bolus. Inotuzumab ozogamicin should not be mixed with other medications. Dosing is based on patient

weight according to the institutional standard; however, doses will be adjusted for patients who experience a  $\geq 10\%$  change in weight from baseline. Please refer to the Dosage and Administration Instructions in the Pharmacy Manual for inotuzumab ozogamicin intravenous solution. Reconstituted inotuzumab ozogamicin will be administered over 1 hour  $\pm 15$  minutes by intravenous infusion unless the subject requires temporary interruption of the administration. A minimum of 6 days should be maintained between the doses.

## 5.1.3 Required Premedication

Recommended premedication before inotuzumab ozogamicin: acetaminophen 650 mg orally, diphenhydramine 10-25 mg IV, hydrocortisone 25 mg IV. Modifications to this premedication are also allowed.

## 5.1.4 Drug Preparation, Storage and Handling

Detailed drug preparation instructions are provided in the Investigator Brochure. Unused portions of the study drug will be discarded properly as per the institutional policies.

**5.2 Bosutinib (BOSULIF®)** is a kinase inhibitor FDA approved for the treatment of adult patients with chronic, accelerated, or blast phase Philadelphia chromosome positive CML with resistance or intolerance to prior therapy. The recommended dose is 500mg once daily with food. Bosutinib will be provided by Pfizer. Bosutinib inhibits the abnormal Bcr-Abl kinase that promotes CML. Modeling studies indicate that bosutinib binds the kinase domain of Bcr-Abl. Bosutinib is also an inhibitor of Src family kinases including Src, Lyn and Hck. Bosutinib minimally inhibits PDGF receptor and c-Kit.

## 5.2.1 Method of Administration

Bosutinib tablets are available containing bosutinib monohydrate equivalent to either 100 or 500 mg of bosutinib. The recommended dose of Bosutinib for the treatment of leukemia is 500 mg by mouth once daily with food. If a dose is missed, the patient should not take an additional dose, but take the usual prescribed dose on the following day. Unused portions of the study drug will be discarded properly as per the institutional policies.

## 6.0 **DOSE MODIFICATIONS**

**6.1** Intrapatient dose reduction will be allowed depending on the type and severity of toxicity. Dose interruption may occur within a cycle until adequate recovery or omission of a dose during a given treatment cycle. While doses given within a treatment cycle (i.e., Days 8 and/or 15) need not be delayed due to neutropenia or thrombocytopenia, dose delays

within a cycle are required for drug-related non hematologic toxicity. The start of the next cycle may be delayed if additional time is required for the patient to recover from study treatment-related toxicity experienced during the current cycle. Delays in start of subsequent cycles greater than 8 weeks should be discussed with the principal investigator. Doses reduced for treatment-related toxicity should not be re-escalated without discussion with the principal investigator.

## 6.2 Recommended dose modifications for inotuzumab ozogamicin-related toxicity

Dose reductions may be required based on the worst toxicity experienced in the previous cycle. Patients experiencing a treatment interruption due to inotuzumab ozogamicin-related toxicity (such as grade 3-4 thrombocytopenia, grade 3-4 transaminitis)  $\geq$ 14 days will be dose reduced as per the Table below. Inotuzumab will be resumed once the toxicity recovers to grade 2 or less. Once a patient has a dose reduction for a drug-related toxicity, the dose will not be re-escalated.

Patients who are unable to tolerate dose level -2 will be withdrawn from treatment unless the PI thinks it is in the best interest of the patient. In that situation, a further 25% dose reduction will be performed.

Dose Level	Cycles 1-6	Cycles 2 to 6 #	Cycles 2 to 6 *
	(in mg/m  )	(in mg/m  )	(in mg/m  )
-2	Day 1 – 0.6	Day 1 – 0.375	Day 1 – 0.5
	Day 8 – Skip	Day 8 – Skip	
	Day 15-0.375	Day 15 – 0.375	
-1	Day 1 – 0.6	Day 1 – 0.375	Day 1 – 0.75
	Day 8 – 0.375	Day 8 – 0.375	
	Day 15-0.375	Day 15 – 0.375	
1	Day 1 – 0.8	Day 1 – 0.5	Day 1 – 1.0
(starting dose level)	Day 8 – 0.5	Day 8 – 0.5	
	Day 15 – 0.5	Day 15 – 0.5	

## Dose Modification table for inotuzumab ozogamicin

# if no peripheral blood blasts; \* once a response is confirmed (CR, CRi, CCyR, and/or absence of MRD by flow cytometry)

## 6.3 Recommended dose modifications for bosutinib-related toxicity

If the toxicities experienced by the patient are thought to be related to bosutinib, the following dose modification criteria will be used-

## Non-Hematologic Bosutinib-related toxicity

Adverse Event	Action #
Grade I	Remain on current dose level
Grade II	For persistent, clinically relevant toxicity not responding to optimal management: Interrupt bosutinib, then reintroduce at the same dose or
	reduce dose by one level upon recovery to grade $\leq 1$
Grade III	For persistent, clinically relevant toxicity not responding to optimal management: Interrupt bosutinib, then dose reduce by 1 level upon recovery to grade $\leq 1$
Grade IV	Interrupt bosutinib. Discuss with PI about resuming bosutinib with appropriate dose reduction. Resumption should happen only upon recovery to grade $\leq 1$

# For subjects who have required a dose reduction due to toxicity, but then have been free of the specific toxicity (grade  $\leq 1$ ) for at least 1 month and are otherwise tolerating bosutinib well, the investigator may choose to re-escalate the dose by one dose level each month (i.e. increase the daily dose by 100 mg/month) until the subject is back to the starting or previous dose (whichever is higher).

NOTE: Cytopenias are common in the patient population studied in this trial. Inotuzumab ozogamicin can cause low platelet count. Therefore, dose modification for bosutinib for hematologic toxicities would be considered only if the investigator and PI strongly feel that the cytopenias were related to bosutinib.

Dose Level	Bosutinib (mg/day) orally once daily
-1	200
1	300
2	400
3	500

## **Dose Modification table for bosutinib**

**6.4** For patients with adverse events that are due to one of the two agents, dose adjustments to only one of the study drugs may be adjusted as per the guidelines mentioned above.

6.5 Dose reductions different than dose described above are acceptable after discussion with the principal investigator and documentation of the rationale for such action.

# 7.0 CONCOMITANT THERAPY

All concomitant medications will be noted in the medical record. All supportive measures consistent with optimal patient care should be provided throughout the study according to the institutional standards.

## 7.1 Allowed Concomitant Therapy

Prophylactic intrathecal therapy is allowed. The use of hematopoietic growth factors or transfusions is allowed. The use of hydroxyurea and/or steroids is permitted for the first 2 weeks of the study period for cytoreduction. Note: Patients with isolated CNS relapse while on the study can continue on the study if deemed in the best interest of the patient. These patients can receive intrathecal chemotherapy to clear the CNS leukemia.

## 7.2 **Prohibited Concomitant Therapy**

Patients may not receive other investigational drugs, immunosuppressive medications (excluding therapy as described in Section 7.1), radiotherapy, or systemic anti-neoplastic therapy during the study. Herbal supplements, including St. John's Wort and grapefruit juice are prohibited.

## 7.3 Concomitant Use With CYP3A Inhibitors

Avoid the concomitant use of strong or moderate CYP3A and/or P-gp inhibitors with bosutinib as an increase in bosutinib plasma concentration is expected. Strong CYP3A inhibitors include ritonavir, indinavir, nelfinavir, saquinavir, ketoconazole, boceprevir, telaprevir, itraconazole, voriconazole, posaconazole, clarithromycin, telithromycin, nefazodone and conivaptan. Moderate CYP3A inhibitors include fluconazole, darunavir, erythromycin, diltiazem, atazanavir, aprepitant, amprenavir, fosamprevir, crizotinib, imatinib, verapamil, grapefruit products and ciprofloxacin.

## 7.4 Concomitant Use With CYP3A Inducers

Avoid the concomitant use of strong or moderate CYP3A inducers with bosutinib as a reduction in exposure is expected. Strong CYP3A inducers include rifampin, phenytoin, carbamazepine, St. John's Wort, rifabutin and phenobarbital. Moderate CYP3A inducers include bosentan, nafcillin, efavirenz, modafinil and etravirine.

# 7.5 Concomitant Use with Proton Pump Inhibitors

Proton Pump Inhibitors decrease bosutinib plasma concentration. Consider using short-acting antacids or H2 blockers instead of PPIs to avoid a reduction in bosutinib exposure. Separate antacid or H2 blocker dosing and bosutinib dosing by more than 2 hours.

## 8.0 STUDY CALENDAR

	Cycle 1	At the start of each subsequent cycle, Day 1 of each cycle (±3 days), Cycle 2-6	At the start of each subsequent cycle, Day 1 of each cycle (±3	
--	---------	--	--	--

						days), Cycle 7 onwards	
Study Assessments 	Screen 	Day 1 	Day 8 (±3 days)	Day 15 (±3 days)	Continuation 	Continuation 	End of Treatm ent Visit 
Informed Consent	Х						
Baseline Demographics	Х						
Medical History	Х						Х
Concomitant Medications	Х			(	Continuous		X
Physical Exam	Х	Х		Х	Х	Х	Х
ECOG Performance Status	Х	Х			Х	Х	X
Vital Signs	Х	Х	Х	Х	Х	Х	Х
Weight	Х	Х			Х	Х	Х
Height	Х						
Hematology, Clinical Chemistry 	Х	X	Х	Х	Х	Х	X
Screening for Hepatitis B, Hepatitis C and HIV	X 						
Pregnancy Test 	Х						
12-Lead ECG	X 						
ECHO or MUGA	$X^7$						
Disease Assessment 	X 				X 	X 	X 
CD22 immunophenotyping	X9				$X^9$	X 	X 
Inotuzumab		Х	Х	Х	X 		
Bosutinib		Continue	ous daily				
Adverse Events				Continuou	S		

- 1. Assessments scheduled on days of dosing should be done prior to administration of study drug(s), unless otherwise specified.
- 2. Within 14 days before first dose. Screening assessments can be used as day 1 assessments if done within 72 hrs.
- 3. If clinically indicated, assessments during Continuation period can occur more frequently.
- Hematology (WBC with differential, unless WBC <0.5 x10^9/L in which case differential not needed), Hemoglobin, Platelet count); Clinical Chemistry (Alanine aminotransferase (ALT), Bilirubin total, Creatinine, uric acid).
- 5. Hematology and Clinical Chemistry will be performed 1 to 3 times weekly during the cycle 1 and at least weekly during the cycles 2-6. For patients who continue bosutinib as maintenance therapy, at least monthly labs are required. Outside labs will be permitted and the PI/treating physician will review the labs for clinical significance, and sign/date the results.
- 6. Perform only in women of child-bearing potential. Pregnancy test can be done in either serum or urine.
- 7. Within 30 days of start of treatment
- 8. Disease assessment by bone marrow samples (aspirate and/or biopsy) should be done at screening, end of cycle 1 (before start of cycle 2), and then before of start cycles 3-6. Note: Once CR/CRi is achieved, bone marrow will repeated every 2 cycles, or as clinically indicated. For patients who continue bosutinib as monotherapy (after completing all 6 cycles of inotuzumab or if inotuzumab is discounted early), bone marrow will be repeated every 3 months. ABL-kinase domain mutation analysis will be performed at baseline (except in patients on the Frontline Ph+ ALL or CML-LBC cohort) and may be repeated after starting treatment, as clinically indicated. Peripheral blood (or bone marrow) PCR for BCR-ABL would be obtained at baseline and prior to start of each cycle.
- 9. CD22 immunophenotyping performed at screening on peripheral blood or bone marrow aspirate. CD22 immunophenotyping will be performed in follow-up bone marrow to assess for minimal residual disease.
- 10. End of Treatment Visit should occur 28 days (±10 days) after last dose of study drugs. For patients who cannot come for the clinic visit, a phone call to assess for any sideeffects will be done. Final study visit assessments will be performed before any other therapeutic intervention, if possible.
- 11. These procedures will not be performed on patients who cannot come to MD Anderson for their final study visit.
- 12. The schedule of Inotuzumab could be days 1, 8, and 15 OR once every 4-weeks (please see Section 4.1 for details)

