## **1.2** Secondary Objectives:

Phase I:

- 1. To determine the efficacy of bosutinib in combination with inotuzumab ozogamicin in patients with Ph+ ALL and CML in lymphoid blast phase that express CD22
- 2. To determine the duration of response of patients treated with this combination
- 3. To determine the overall survival of patients treated with this combination
- 4. To determine the effect of the level of pre-treatment expression of CD22 with response to this combination
- 5. To determine the efficacy of this combination according to pre-treatment mutation status in the abl kinase domain
- 6. To determine the minimal residual disease after treatment with this combination and its impact in long-term outcome

Phase II:

- 1. To determine the safety bosutinib in combination with inotuzumab ozogamicin in patients with Ph+ ALL and CML in lymphoid blast phase that express CD22
- 2. To determine the duration of response of patients treated with this combination
- 3. To determine the overall survival of patients treated with this combination
- 4. To determine the effect of the level of pre-treatment expression of CD22 with response to this combination
- 5. To determine the efficacy of this combination according to pre-treatment mutation status in the abl kinase domain
- 6. To determine the minimal residual disease after treatment with this combination and its impact in long-term outcome

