## 3.1 Inclusion Criteria

1. Relapsed or refractory B-cell ALL or CML in lymphoid blast phase. Philadelphia chromosome must be present at screening (as determined by cytogenetic analysis, FISH, or PCR [i.e., BCR-ABL positive]). Note: patients with CML who have received treatment with tyrosine kinase inhibitors for their CML, and have progressed to lymphoid blast phase are eligible for frontline treatment.

Frontline Ph+ ALL or CML-LBC Cohort: Patients with newly-diagnosed Ph+ ALL or CML-LBC, who have received no or minimal treatment (minimal treatment is defined as treatment with steroids/hydroxyurea of  $\leq 2$  week duration; vincristine  $\leq 2$  doses; tyrosine kinase inhibitor of  $\leq 4$  week duration;  $\leq 2$  doses of cytarabine) and are  $\geq 60$  years or older are eligible. Patients must have bone marrow blasts >5% at the time of screening.

2. Expression of CD-22 in  $\geq$ 20% blasts

3. Age 18 years or older (For Frontline Ph+ ALL or CML-LBC Cohort: Age 60 years or older)

- 4. Eastern Cooperative Oncology Group (ECOG) Performance Status score of  $\leq 2$
- 5. The following baseline laboratory data:
  - Serum bilirubin  $\leq 2.0 \text{ mg/dl}$
  - Serum creatinine  $\leq 2.0 \text{ mg/dl}$
  - Alanine aminotransferase (ALT) and aspartate aminotransferase (AST)  $\leq 3 \times 10^{-10}$  x upper limit of normal (ULN)

6. Females of childbearing potential must have a negative serum or urine beta human chorionic gonadotrophin ( $\beta$ -hCG) pregnancy test result within 14 days prior to the first dose of study drugs and must agree to use one of the following effective contraception methods during the study and for 30 days following the last dose of study drug. Effective methods of birth control include:

- birth control pills, shots, implants (placed under the skin by a health care provider) or patches (placed on the skin)
- Intrauterine devices (IUDs)

• condom or occlusive cap (diaphragm or cervical/vault caps) used with spermicide Females of non- childbearing potential are those who are postmenopausal greater than 1 year or who have had a bilateral tubal ligation or hysterectomy.

7. Males who have partners of childbearing potential must agree to use an effective contraceptive method during the study and for 30 days following the last dose of study drug

8. Patients or their legally authorized representative must provide written informed consent

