- **4.1.1.4 Transition to the every 4-weekly schedule** In order to decrease the toxicity of the subsequent cycles, once a response is confirmed (CR, CRi, or whenever CCyR and/or absence of MRD by flow cytometry is documented), subsequent cycles will be administered at a dose of 1.0 mg/m^2 once every 4 weeks. Note: Patients who have been switched to every 4 weeks schedule may return to the weekly schedule if there is concern about recurrence of the disease.
- **4.1.1.5** Patients who experience a clinical benefit (CR/CRi/PR) with acceptable toxicity can receive up to a total of 6 cycles of inotuzumab ozogamicin. Treatment with bosutinib should continue indefinitely as long as patient is tolerating it well and responding to it.
- **4.1.1.6** Bosutinib will be dose-escalated in subsequent cohorts in a standard 3+3 study design (see Section 11.2).

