**Transition to the every 4-weekly schedule** – In order to decrease the toxicity of the subsequent cycles, once a response is confirmed (CR, CRi, or whenever CCyR and/or absence of MRD by flow cytometry is documented), subsequent cycles will be administered at a dose of 1.0 mg/m^2 once every 4 weeks. Note: Patients who have been switched to every 4 weeks schedule may return to the weekly schedule if there is concern about recurrence of the disease.

Patients who experience a clinical benefit (CR/CRi/PR) with acceptable toxicity can receive up to a total of 6 cycles of inotuzumab ozogamicin. Treatment with bosutinib should continue indefinitely as long as patient is tolerating it well and responding to it.

NOTE: For all patients included in this trial, inotuzumab doses may be omitted if deemed in the best interest of the patient (for e.g. patients with plans of undergoing stem cell transplant) by the treating physician (after discussion with the study PI). The reason for omission will be noted in the medical record. Patients who achieve MRD negative remission may have further doses of inotuzumab omitted, if deemed in the best interest of the patient by the treating physician (in discussion with the study PI).

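### The MRD assessment rests on CD22, the antigen that inotuzumab targets, so low-level CD22-negative disease could be counted as MRD-negative in secondary objective 6

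*Combined protocol and SAP*

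**What the plan says.** Secondary objective 6, in both phases (Section 1.2), is "To determine the minimal residual disease after treatment with this combination and its impact in long-term outcome". The only sentence that ties an assay to MRD is note 9 of the Study Calendar (Section 8.0): "CD22 immunophenotyping will be performed in follow-up bone marrow to assess for minimal residual disease". The calendar has a single immunophenotyping row, and it is labelled CD22.

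Section 5.1 describes inotuzumab as an antibody that "recognizes CD22 antigen and is covalently linked via an acetyl butyrate linker" to its toxin. Inclusion criterion 2 (Section 3.1) asks for "Expression of CD-22 in" at least 20% of blasts.

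A test that does not depend on CD22 is already scheduled in note 8: "Peripheral blood (or bone marrow) PCR for BCR-ABL would be obtained at baseline and prior to start of each cycle". Nothing links it to MRD status.

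MRD is also mentioned in the treatment sections. Section 4.1.1.4 changes the inotuzumab schedule on CR, CRi, or "whenever CCyR and/or absence of MRD by flow cytometry is documented"; Section 4.1.1.7 and the footnote to the inotuzumab dose modification table in Section 6 use similar wording. The note at the end of Section 4.1.1.7 says "Patients who achieve MRD negative remission may have further doses of inotuzumab omitted", at the physician's discretion. Sections 4.1.1.3 and 4.1.1.7 give evidence of MRD as an example of a reason to modify the count-recovery guidelines.

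Section 9.0 defines MaHR, CR, CRi and PR, but not MRD. Section 11 gives no MRD panel, sensitivity or negativity threshold.

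**The concern.** A CD22-directed conjugate would be expected to spare cells with little or no CD22. A residual-disease read that finds leukemic cells by the same antigen can therefore lose sensitivity because of the treatment, in the direction that flatters the regimen. The low entry threshold adds to this, because a patient may start with most blasts already CD22-negative.

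At stake is objective 6. A patient in remission with residual CD22-negative disease would sit in the MRD-negative group. The reported MRD-negative rate would be too high, and that group would mix cleared and uncleared patients. If the residual cells carry relapse risk, the outcome contrast between MRD-negative and MRD-positive patients would tend to shrink.

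**Working it through.** The plan states no figure for MRD, so there is none to reproduce. The check covers what the documents imply about the size of the problem.

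**1. Largest CD22-negative share at entry.** From inclusion criterion 2: 100% − 20% = 80%. This is the maximum at the threshold. The documents do not give the baseline distribution of CD22 among enrolled patients.

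**2. CD22-negative share of residual blasts (illustration).** Let f be the CD22-positive fraction at entry, and kp and kn the log10 kill of CD22-positive and CD22-negative blasts. Then

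share = (1 − f)·10^(−kn) / [f·10^(−kp) + (1 − f)·10^(−kn)] = (1 − f) / [f·10^(−d) + (1 − f)], with d = kp − kn.

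Only the difference d matters, so the same shares apply at any depth of response, including below the morphologic limit. The values of f above 20% and all values of d are assumptions; the documents supply none.

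| f at entry | d = 0 | d = 1 | d = 2 |
|---|---|---|---|
| 20% | 80% | 0.8/0.82 = 97.6% | 0.8/0.802 = 99.75% |
| 50% | 50% | 0.5/0.55 = 90.9% | 0.5/0.505 = 99.0% |
| 90% | 10% | 0.1/0.19 = 52.6% | 0.1/0.109 = 91.7% |

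Over this grid, a read that counted only CD22-positive cells would miss between a tenth and nearly all of the residual blasts. This is a share of cells, not the probability that a patient is misclassified. Misclassification needs the CD22-positive residue to fall below the negativity threshold while the total residue stays at or above it, and the plan states no threshold.

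**3. Effect on the reported rate.** If m patients are misclassified out of R in the denominator, the MRD-negative rate is overstated by m/R. The plan does not fix R. With all 28 Phase II patients in a cohort, one patient is worth 1/28 = 3.6 percentage points. With 12 responders, the smallest number that meets the final decision rule, one patient is worth 1/12 = 8.3 points.

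**4. What is not affected.** The Phase II primary endpoints are MaHR and CR/CRi (Section 11.1.1), neither of which uses MRD. The two-stage rule in Section 11.2 (stop if 3 or fewer of 12 respond; active if 12 or more of 28 respond) gives an exact binomial early-termination probability of 0.4925 at a true rate of 30%, against the stated 49%. The type I error is 0.0954 (limit 0.10) and the power at 50% is 0.8020 (target 0.80). These figures stand whatever is done about MRD.

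**The case against.** The strongest reply is that note 9 names a test, not a gating rule. It may be shorthand for a broader flow panel that includes CD22, and Section 4.1.1.4 speaks of flow cytometry without mentioning CD22. This stands, and it limits the point to what could happen under the stated method. If a broader panel is intended, note 9 misdescribes it and still needs correction.

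A reader might infer three stronger things that the documents do not support.

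- **CD22-negative residual leukemia is read as MRD-negative under the plan.** That would require CD22 to be the sole gate for a positive call, and nothing says so.
- **A patient could be called MRD-negative with most of the starting leukemia still present.** CR and CRi need marrow blasts of 5% or less, and marrow is assessed after cycle 1 and before cycles 3 to 6 (every two cycles once CR/CRi is reached). Gross disease would normally fail on morphology. Bosutinib also acts on BCR-ABL, which all patients carry at entry, so CD22-negative blasts are not left untreated.
- **A false-negative read would drive treatment.** CR, CRi or CCyR each trigger the schedule change alone, and patients may return to the weekly schedule. Dose omission requires remission, is discretionary and follows discussion with the principal investigator, while BCR-ABL PCR is drawn before each cycle.

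It is also fair to say that MRD is not a listed endpoint in Section 11.1 and that Section 11.3 treats secondary analyses as exploratory. This lowers the weight of the point but does not remove it: objective 6 is stated for both phases, and a bias that favours the regimen is unwelcome in an exploratory result too.

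**Conclusion.** The point holds in conditional form. The only assay the plan assigns to MRD is built on the antigen its antibody-drug conjugate targets, in patients who may enter with up to 80% CD22-negative blasts. If CD22 is used to identify residual blasts, low-level CD22-negative disease in morphologic remission could be counted as MRD-negative. The bias would be toward overstated clearance, with a distorted MRD-outcome association in objective 6.

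The size is unknown. It depends on the baseline CD22 distribution, the difference in kill between CD22-positive and CD22-negative blasts, the panel and the threshold, and the documents give none of these apart from the entry minimum. Greater survival of CD22-negative cells is an inference from mechanism. It is not a figure in the plan. The primary endpoints, sample size and stopping rules are unaffected. The change is worth making because a better read is available from samples already scheduled.

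**What to change.** For objective 6, change note 9 along these lines: MRD is assessed on the scheduled follow-up marrow by multiparameter flow cytometry with gating that does not depend on CD22; CD22 expression on any residual blasts is reported separately and is not used to call MRD.

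State the panel, its sensitivity and the negativity threshold. Report the BCR-ABL PCR from note 8 side by side with flow, showing concordant and discordant results. Record whether each PCR sample was blood or marrow, since note 8 allows either. Note 8 also allows a biopsy without an aspirate, so a visit with no usable flow sample should be reported as not assessed and not as negative.

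The sponsor must reconcile the MRD wording in Sections 4.1.1.3, 4.1.1.4, 4.1.1.7, the Section 6 inotuzumab table footnote and Section 8.0 notes 8 and 9. No change to a dosing or omission rule is proposed here.

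The cost is wording and a panel specification, with no new scheduled sampling. The downside is a possibly lower reported MRD-negative rate.
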